#### **4.4.2. Windows Periods**

Before analyzing the data, all post-Baseline visits (scheduled or unscheduled, unless specified otherwise) will be mapped to an analysis visit based on the windowing algorithm in Section 15.5 Analysis window Details. If multiple visits containing the same data of interest can be mapped to the same analysis visit, the visit closest to the target day will be used in the analysis. In the event that two or more visits are equidistant to the target day, the later visit will be used in the analysis.

Please refer Section 0 for details of Analysis Window.

#### **4.4.3. Definition of Baseline**

Baseline value is the last available value prior to the first dose of study drug or randomization date, in case patient is not exposed. The baseline for weekly average pruritus NRS score is defined as the average of daily non-missing scores obtained during the 7 days prior to randomization. A minimum of 4 daily scores out of the 7 days is required to calculate the baseline average score

#### **4.4.4. Study Day Calculation**

Study days are calculated considering Day 1 as the day of first administration of intervention (or the day of randomization for patient not exposed).

If the event is after the reference start date (date of drug administration) then the study day will be calculated as assessment date – date of drug administration + 1 else if event is prior to the reference start date then it will be calculated as assessment date – date of drug administration.

Summary statistics for data such as adverse events and concomitant medications will not be reported by visit.

#### **4.4.5. Pre-specified Subgroups**

The following subgroups will be explored for the primary endpoint and selected key secondary endpoints:

1. Age (<65, >=65)
2. Gender (male, female)
3. Race
4. Region (ASIA-PACIFIC, EMEA, NORTH AMERICA)
5. Weight (<median, >=median)
6. EASI (<=21 vs >21) from eCOA, per baseline definition in Section 4
7. IGA (3 vs 4) from eCOA, per baseline definition in Section 4
8. Previous systemic immunosuppressant use (Yes vs No)
9. Previous biologic use (Yes vs No)
10. Previous dupilumab use (Yes vs No)
11. Previous cyclosporine use (Yes vs No)
12. Previous methotrexate use (Yes vs No)

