LTE enables all enrolled patients to have an opportunity to receive treatment at doses expected to elicit a meaningful clinical response (based on observations from the Phase 2a KY1005-CT02 study). Patients who achieve ≥ EASI 75 or who attain IGA 0/1 at Day 169 (Week 24) will be randomised 3:1 to either enter a maintenance withdrawal phase or continue on their pre-Week 24 dose/interval. The purpose being to characterise the durability of response in conjunction with PK following treatment discontinuation in those withdrawn from therapy and to assess the clinical response and long-term safety in those continuing to receive Q4W treatment at their pre-Week 24 dose. Those patients who are re-randomised at Day 169 (Week 24) and who subsequently lose clinical response, defined during that study period as the first instance of < EASI 50 and where rescue therapy is no longer permitted as per Section 5.3.4 on or after the Day 197 (Week 28) study visit, will be offered the opportunity to receive retreatment with KY1005 in the LTE study. Results from this randomised withdrawal maintenance phase will inform the subsequent later stage development of KY1005 in the treatment of AD. At Day 365 (Week 52), patients who complete the second study period without loss of clinical response will have an additional 112 days' safety follow-up to Day 477 (Week 68) and will then be discharged from the study. The last dose will be administered no later than Day 337 (Week 48). If during safety follow-up or after the end of study this cohort of patients experience worsening of their AD, and in the investigator's opinion re-treatment with KY1005 is considered appropriate, they may be considered for enrolment in the LTE (subject to meeting inclusion/exclusion criteria). **Number of subjects:** A total of 350 patients (approximately 70 patients per treatment arm) will be randomised. **Study population:** Adult patients with moderate-to-severe AD who have a documented history, within 6 months prior to Baseline, of either inadequate response to topical treatments or inadvisability of topical treatments (eg, not well tolerated). **Key inclusion criteria:** Patients must fulfil all the following inclusion criteria for entry into the study: 1. Adults (18 to <75 years of age) with AD, as defined by the American Academy of Dermatology Consensus Criteria, for 1 year or longer at Baseline (Day 1; prior to first administration of IMP). For United Kingdom, see Section 17.15.2 (Appendix 15). 2. EASI of 12 or higher at the Screening Visit and 16 or higher at Baseline. 3. IGA of 3 or 4 at Baseline. 4. AD involvement of 10% or more of BSA at Baseline. 5. Baseline worst/maximum pruritus NRS of ≥4. The Baseline weekly average of daily worst/maximum pruritus NRS will be calculated from the 7 consecutive days immediately preceding the Baseline visit. A minimum of 4 daily scores out of the 7 will be required.

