Patients fulfilling any of the following criteria will be excluded from the study:

- 1. Treatment with any of the following prior to first IMP administration (Baseline):
 - Systemic corticosteroids, and systemic calcineurin inhibitors (tacrolimus and cyclosporin)
 - Leukotriene inhibitors
 - Systemic therapy for AD, including but not limited to methotrexate, cyclosporine, azathioprine, phosphodiesterase type 4 (PDE4)-inhibitors, IFN-γ and mycophenolate mofetil (except for the drugs mentioned on other criteria with specific washout periods);
 - Targeted biologic and small molecule treatments
 - Previous treatment with systemic janus kinase (JAK) inhibitors
 - Topical corticosteroids, tacrolimus or pimecrolimus, or topical PDE4

Property of the Sanofi Group - strictly confidential

PAGE 12 OF 147

- 1-Mar-2022 Version number: 1
- Prescription or non-prescription moisturisers with additives (eg, urea, filaggrin)
- Phototherapy or allergen immunotherapy
- o Regular use (>2 visits/week) of a tanning booth/parlour
- o Any prior use of anti OX40 or anti OX40L mAb, including KY1005.
- o Investigational therapy for the treatment of AD or other conditions within 5 half-lives or the limit of PD effects or 12 weeks where the $t_{1/2}$ is unknown
- Known history of, or suspected, significant current immunosuppression, including history of invasive opportunistic or helminth infections despite infection resolution or otherwise recurrent infections of abnormal frequency or prolonged duration.
- 3. Weight <40 kg or >150 kg at Baseline.
- 4. Treatment with a live (attenuated) immunisation within 12 weeks prior to Baseline; completion of required administrations of COVID-19 vaccine within 14 days prior to Baseline or within 14 days immediately prior to or following IMP administration.
- 5. Men and women (of reproductive potential) unwilling to use birth control and women who are pregnant or breastfeeding.
- 6. Any malignancies or history of malignancies prior to Baseline (except for non-melanoma skin cancer that has been excised and cured for more than 3 years prior to Baseline; in situ cervical carcinoma that has been excised and cured).
- 7. Positive for human immunodeficiency virus, hepatitis B surface antigen, hepatitis B core antibody or hepatitis C antibody at the Screening Visit.
- 8. History (within last 2 years prior to Baseline) of prescription drug or substance abuse, including alcohol, considered significant by the Investigator.

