Absolute and percentage change in SCORAD Index from Baseline to Day 169 (Week 24) and over time. Absolute and Percentage change in affected BSA from Baseline to Day 169 (Week 24) and over time. Absolute and Percentage change in POEM from Baseline to Day 169 (Week 24) and over time. • Absolute and Percentage change in DLQI from Baseline to Day 169 (Week 24) and over time. Absolute and Percentage change in ADCT from Baseline to Day 169 (Week 24) and over time. Absolute and Percentage change in HADS from Baseline to Day 169 (Week 24) and over time. • Absolute and Percentage change in weekly average of pruritus NRS from Baseline to Day 169 (Week 24) and over time. • Proportion of patients with improvement (reduction) of weekly average of pruritus NRS ≥3 with a Baseline pruritis NRS of ≥3 from Baseline to Days 113 (Week 16) and 169 (Week 24). PD endpoints: Anti-KY1005 antibody titre and number of patients with positive response. Main exploratory endpoints: **Statistical analysis:** Sample Size: A sample size of 350 patients (70 patients / treatment arm) in the target population, (adults with moderate-to-severe AD who have a documented history, within 6 months prior to Baseline, of either inadequate response to topical treatments or inadvisability of topical treatments), randomised 1:1:1:1:1 to 4 KY1005 groups or Placebo group is estimated to provide at least 84% power to detect a pairwise difference in means between each KY1005 and Placebo with respect to the percentage change in EASI from Baseline to Day 113 (Week 16), based on a 2-sided 2-sample equal-variance t-test. **Analysis Sets:** Efficacy Analysis Set: The full analysis set (FAS) includes all randomised patients. Efficacy analysis will be based on treatment allocated at randomisation and stratified by disease severity (moderate/severe) and region. Methods: Statistical analysis of all endpoints will be defined in detail in the Statistical Analysis Plan. For continuous variables, descriptive statistics will include: the number of patients, mean, median, standard deviation, minimum, and maximum. For categorical or ordinal data, frequencies and percentages will be displayed for each category.

1-Mar-2022

Efficacy Analyses:

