## 2. Objectives

### 2.1. Primary objective and Endpoints

Objective	Endpoint
To characterise the efficacy (including dose/exposure-response) across a range of KY1005 exposures compared to Placebo on the signs of AD using the Eczema Area and Severity Index (EASI) in those patients who have a documented history, within 6 months prior to Baseline, of either inadequate response to topical treatments or inadvisability of topical treatments	
 
Percentage change in EASI from Baseline to Day 113 (Week 16).
 

[figure not shown]

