A table, figure, listing is to be generated for any required item even where no data is available or reported. This will ensure the health authorities that the tables, figures, listings and narratives are accounted for. This table, figure or listing will state: “No Data Reported”.

All other statistical analyses performed in part 1 will be performed using a two-sided hypothesis test at the overall 5% level of significance.

P-values will be rounded to four decimal places. If a rounded P-value is less than 0.0001 it will be reported as “<0.0001.”

Unless otherwise specified, baseline will be defined as the last non-missing evaluation prior to study drug administration.

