### **Subgroup analysis of primary endpoint**

The primary efficacy endpoint will also be analysed for the pre-specified subgroups as specified in Section 4.4.5. The analyses for the subgroup population will be performed with the primary Estimand (Estimand 1) for the primary endpoint regarding the intercurrent events and missing data handling, and population level summary. In each subgroup, the treatment effects for the primary endpoint will be provided, as well as the corresponding 95% CI.

Interaction effects will be tested using the ANCOVA model between treatment arms and subgroup factor. The model will include all the covariates in the main statistical model plus the subgroup variable and the subgroup-by-treatment interaction. A p-value for the test of interaction will be provided.

Forest plot will be provided to present the estimates and the corresponding 95% CI for each subgroup.

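### In the readable SAP, interaction with age, weight and baseline EASI is tested only on two-way cuts; an exploratory test on the continuous values should be added beside them

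*SAP*

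**What the plan says.** SAP 4.4.5 lists subgroups to be explored for the primary endpoint and selected key secondary endpoints. Three of them are two-level versions of continuous baseline variables:

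- weight: "Weight (<median, >=median"
- baseline EASI: "EASI (<=21 vs >21) from eCOA"
- age: below 65 against 65 and over.

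For the primary endpoint, SAP 8.1 (subgroup analysis) states: "Interaction effects will be tested using the ANCOVA model between treatment arms and subgroup factor". The subgroup variable and its interaction with treatment are added to the main ANCOVA, a p-value is reported, and a forest plot shows each subgroup's effect with its 95% CI. For the two key secondary endpoints with subgroup analyses (EASI 75 and IGA 0/1 at Week 16), SAP 8.2 plans estimates and forest plots and mentions no interaction test.

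Protocol 10.4.2 already has the continuous baseline value in the ANCOVA, but as a main effect only. The EASI boundary of 21 is the one that defines the moderate and severe randomisation strata (SAP 3.1). Eligible patients are 18 to <75 years old with baseline EASI of 16 or more (Protocol 4.2), and the exclusions include "Weight <40 kg or >150 kg at Baseline" (Protocol synopsis).

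**The concern.** Doses are fixed in mg, and eligible weights span 150/40 = 3.75-fold. If the effect changes with weight, it would more plausibly do so gradually than in a step at the sample median. The same holds for age and baseline severity. A two-way cut treats a 40 kg patient and one just under the median as identical, and so discards information that is already collected.

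The age cut is the weakest of the three. Only a ten-year band of the eligible range lies at or above 65, so one side of a five-arm comparison may hold a handful of patients per arm.

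The plan gives no reason for testing on the cuts alone. The primary objective is "To characterise the efficacy (including dose/exposure-response) across a range of KY1005 exposures", and Protocol 3.3 says the interim analysis is to inform phase 3 planning. A non-significant interaction on a coarse cut could then be taken as reassurance that the effect is even across weight, age and severity, when the test had little chance of showing otherwise.

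**Working it through.** **Inputs from the documents**

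- Sample size: "A total of 350 patients (approximately 70 patients per treatment arm) will be randomised" (Protocol synopsis), in five arms.
- Level: "two-sided hypothesis test at the overall 5% level of significance" (SAP section 4).
- A two-level or linear covariate crossed with five arms gives a 4-df interaction test.
- Phase 2a 95% CIs for percentage change in EASI (Protocol Table 1-1).

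**Assumptions, because the documents give no figure**

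- Residual SD of 40 percentage points.
- A linear gradient of b points per covariate SD, equal in the four active arms and zero on placebo.
- The distributions of weight, EASI and age.
- Complete data on 70 per arm.

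**1. The plan's own power figure.** The synopsis claims "at least 84% power to detect a pairwise difference in means between each KY1005 and Placebo". The difference and SD behind it are redacted, so it cannot be reproduced from the documents. An assumed difference of 20 points with SD 40 (standardised effect 0.50) and 70 per arm gives 83.6% by the t-test, which is compatible. No power is stated for any interaction.

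**2. SD.** CI half-width / 1.99 x sqrt(n):

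- low dose: 15.435/1.99 x sqrt(27) = 40.3
- high dose: 15.07/1.99 x sqrt(27) = 39.3
- placebo: 16.65/1.99 x sqrt(24) = 41.0.

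**3. Noncentrality with the continuous covariate.** The mean slope over five arms is 0.8b. The sum of squared deviations is (0.8b)^2 + 4 x (0.2b)^2 = 0.80b^2. So lambda = 70 x 0.80b^2 / 40^2 = 0.035b^2, which is 0.875, 3.5 and 11.34 at b = 5, 10 and 18.

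**4. Effect of the cut.** Lambda is multiplied by the squared correlation between the covariate and its two-level version:

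- Weight, median split: 2/pi = 0.64 for a normal covariate; 0.62 to 0.65 over the shapes tried.
- EASI at 21, skewed upward from 16: 0.24 to 0.42 (0.30 when 77% lie above 21, 0.24 when 84% do).
- Age at 65: 0.09 to 0.30 when 1% to 9% are 65 or over. For example, a normal with mean 38 and SD 15, truncated to 18 to <75, has about 3.2% at or above 65, or 70 x 0.032 = 2.3 patients per arm.

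**5. Power** (noncentral F with 4 and 350 - 14 = 336 df, 5% level)

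| b per SD | Continuous | Weight cut | EASI cut | Age cut |
|---|---|---|---|---|
| 5 | 10% | 8% | 6-7% | 5-6% |
| 10 | 28% | 18-19% | 10-13% | 7-11% |
| 18 | 77% | 54-56% | 22-37% | 11-27% |

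Power of 80% with the continuous covariate needs lambda = 12.1, so b = sqrt(12.1/0.035) = 18.6. Power of 90% needs 15.6, so b = 21.1. Between those two points the loss is 18-23 points for weight, 40-60 for EASI and 51 to about 78 for age. If age were uniform over the eligible range, its loss would be 38-39.

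**6. Simulation check** (1,500 runs per case, continuous against cut)

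| b per SD | Weight | EASI | Age |
|---|---|---|---|
| 10 | 27% v 19% | 28% v 11% | 30% v 8% |
| 18.5 | 76% v 55% | 77% v 29% | 78% v 12% |

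At b = 5 each loss is 2-3 points.

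**7. How steep these gradients are.** The Phase 2a differences from placebo were 69.97 - 49.37 = 20.6 and 80.12 - 49.37 = 30.8 points. At b = 18 the effect would fall to zero at 20.6/18 = 1.1 to 30.8/18 = 1.7 SD from the mean.

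**The case against.** The other side has a good deal in its favour.

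- **Steepness.** A reader might infer that the cuts cost 20 to 70 points of power whatever the truth. They do not. Losses of that size need a gradient about as large as the whole Phase 2a treatment effect. At b = 18, two SDs in the favourable direction would imply a total reduction of 49.37 + 20.6 + 36 = 106% or more, which is past the 100% floor. At gentler gradients both tests are weak. This stands.
- **Weight.** A reader might infer that weight, the natural example under fixed doses, suffers most. Its loss peaks at about 21-23 points; the largest losses come from age. Protocol 1.4.1.2 also reports no meaningful difference between two Phase 2a regimens 2.5-fold apart in dose, with the lower one numerically better. That argues against a steep weight gradient, though with 27 patients per arm it does not exclude one. This stands.
- **Assumed distributions.** The EASI and age distributions are not in the documents, so those losses are ranges under assumption. This stands.
- **EASI at 21.** It is the stratum boundary, so reporting by it is ordinary practice. This is a reason to keep the cut, but not a reason to have no other test.
- **Exploratory status.** SAP 4.4.5 says the subgroups will be explored. No interaction power is promised, and the forest plot would show a wide interval for patients aged 65 or over. This limits the importance of the point but does not remove it, because SAP 8.1 still commits to the p-values.
- **Text that cannot be read.** Exploratory objectives and parts of the estimand tables are redacted, and population PK has its own plan (SAP section 10). A reader might infer that the gradient with weight is examined nowhere; the documents do not allow that conclusion.
- **Shape.** A true step at the cut would favour the cut. This stands.

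**Conclusion.** The point holds as a cheap improvement to an exploratory analysis. In the readable text, the primary-endpoint interaction tests for age, weight and baseline EASI use only two-way cuts. Against a roughly linear gradient these have less power than a test on the continuous value, and the age test is close to uninformative.

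The size is conditional. With SD 40, 70 complete patients per arm and roughly 18-22 points per SD, the loss is about 20 points for weight, 40-60 for EASI and 50-78 for age. At 10 points per SD it is about 8, 17 and 20 points, with only 27-30% power even for the continuous test. At 5 points per SD it is 2-4. Missing data would weaken both tests: if only the 49 per arm assumed in Protocol 3.6 for Week 24 contributed, the gradients needed for 80-90% power would rise by sqrt(70/49) = 1.2.

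A reader might go further and conclude that the cuts should be dropped or that the primary analysis is affected. Neither follows. The primary comparisons do not use these subgroup factors, and the cuts have a descriptive purpose.

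**What to change.** In SAP 8.1, keep the planned categories, forest plots and interaction tests, and add text along these lines:

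*For age, weight and baseline EASI, an additional exploratory interaction p-value will be obtained from the primary ANCOVA with the continuous baseline value and its interaction with treatment. The estimated difference from placebo, with 95% CI, will be given for each KY1005 regimen at the 10th, 50th and 90th percentiles of the covariate. A non-significant interaction on the categorised factor will not be taken as evidence of a consistent effect.*

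The categorical factors (sex, race, region, IGA, prior therapies) stay as they are. Baseline EASI is already a covariate, so only its interaction term is new.

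The cost is a short SAP paragraph and three extra model fits on data already collected; the primary analysis does not change. There are three downsides. The added test assumes a roughly linear gradient on a bounded outcome, it may be sensitive to extreme values (weight especially), and its p-value does not come from the same model as the forest plot, so the two should be labelled separately.

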#### 4.4.6. Duration (e.g., for Adverse Events)

If date is collected, then duration is calculated as event end date minus event onset date + 1. Unit is days.

#### 4.4.7. Coding Dictionaries

Adverse events, medical history and prior and concomitant non-drug treatment procedures will be coded using the Medical Dictionary for Regulatory Activities (MedDRA) Version 24.1 or later.

Previous and concomitant treatments will be coded with the WHODRUG Global B3 March 2021 or later.

#### 4.4.8. Efficacy Parameters

Below efficacy parameters will be analyzed:

##### 1. Eczema Area and Severity Index (EASI)

The EASI is a validated measure used in clinical practice and clinical trials to assess the severity and extent of AD (Hanifin 2001). The EASI score calculation is based upon the Physician's Assessment of Individual Signs [erythema (E), induration/papulation (I), excoriation (X), and lichenification (L)], where each sign is scored as 0 = Absent, 1 = Mild, 2 = Moderate, or 3 = Severe, and also upon the Area Score [based on the % (BSA) affected] where 0 = 0% BSA, 1 = 1-9% BSA, 2 = 10-29% BSA, 3 = 30-49% BSA, 4 = 50-69% BSA, 5 = 70-89% BSA, 6 = 90-100% BSA.

For each of major section of the body (head, upper extremities, trunk and lower extremities), EASI score = (E+I+X+L) x Area Score. The total EASI score is the weighted total of the section EASI using the weights 10% = head, 20% = upper extremities, 30% = trunk, 40% = lower extremities. The minimum possible EASI score is 0 and the maximum possible EASI score is 72 where a higher score indicates increased extent and severity of atopic dermatitis. The EASI score of each sign (E, I, X and L) can be calculated in a similar way, for example, the EASI score of erythema = weighted sum of E x Area Score at each section

##### 2. Investigator's Global Assessment (IGA)

The IGA is a static 5-point measure of AD disease severity used in clinical studies to determine severity of AD and clinical response to treatment. The ratings (0 = clear, 1 = almost clear, 2 = mild, 3 = moderate, 4 = severe) are an overall assessment of AD skin lesions based on erythema and papulation/infiltration. IGA score will be assessed at every scheduled and unscheduled clinic visit.

